- To assess tumor site immune phenotype, T cell repertoire and PD L1/2 expression when tissue available for biopsy prior to autologous transplant conditioning and

then at time of progression (within 18 months) after autologous transplant conditioning.

The tertiary objectives are:

• To identify specific intestinal microbial strains associated with improved outcome in autologous stem cell transplantation patients treated with combined checkpoint inhibitors. The overall microbial composition in stool samples of patients will be analyzed at screening, preconditioning (to be collected within 48 hours prior to transplant admission), at engraftment (within 72 hours of ANC ≥ 500), and then serially, on day 1 of week 1 (to be collected within 48 hours prior to clinic visit) and then weeks 4, 7, 12, 18, and 26, End of Treatment and 9, 12, 15 and 18 months post-transplant, and at time of relapse, as it occurs. A 16S ribosomal RNA (rRNA) miSeq Illumina platform will be used for overall microbial composition and quantitative real-time PCR analysis will validate the specific microbial strains identified by miSeq.

Phase IIA

The primary objectives of this study are:

• To assess progression-free survival at 18 months after ASCT in patients in cohorts that were deemed safe in Phase Ib (no more than 3 treatment-related toxicity) and at least 4 of 7 patients progression free at 18 months in the Phase Ib.

The secondary objectives of this study are:

- To assess complete response rate at 3, 6 and 12 months after ASCT in patients at high risk for post-transplant recurrence including patients in the successor expansion cohorts following the Phase Ib trial.
- To assess progression-free survival at 12 months after ASCT in patients at high risk for post-transplant recurrence including patients with in the successor expansion cohorts following the Phase Ib trial.
- Determine the toxicities resulting from administration of the treatments in patients enrolled in the successor expansion cohorts following the Phase Ib trial.
- To assess blood immune reconstitution, phenotype and TCR repertoire at screening (at time of informed consent), at apheresis (stem cell collection), and then serially the day 1 of week 1 of combined checkpoint inhibitors and then weeks 4, 7, 12, 18 and 26, End of Treatment, and at 9, 12, 15, and 18 months post-transplant and at time of relapse, as it occurs.

The tertiary objectives are:

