• To identify specific intestinal microbial strains associated with improved outcome in autologous stem cell transplantation patients treated with combined checkpoint inhibitors.

The overall microbial composition in stool samples of patients will be analyzed at screening, preconditioning (to be collected within 48 hours prior to transplant admission), at engraftment (within 72 hours of ANC \geq 500), and then serially, on day 1 of week 1 (to be collected within 48 hours prior to clinic visit) and then weeks 4, 7, 12, 18, and 26, End of Treatment, and 9, 12, 15 and 18 months post-transplant, and at time of relapse, as it occurs.

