- 2. Within each subset, the following separate longitudinal analysis of cell counts over time will conducted:
 - i. Count of dendritic cells as a function of time (14 timepoints) and status (DC1 versus DC2).
 - ii. Count of DC2 as a function of time (14 timepoints) and PDL-1+/- status,
 - iii. Count of macrophages as a function of time (14 timepoints) and status (M1 versus M2)
 - iv. Count of M2 cell as a function of time (14 timepoints) and PDL-1+/- status,
 - v. Count of CD4 T cells as a function of time (14 timepoints) and follicular helper function status.
 - vi. Count of T cells as a function of time (14 timepoints) and activated status (activated versus naïve),
- vii. Count of activated T cells as a function of time (14 timepoints) and PD1+/- status,
- viii. Count of Tregs as a function of time (14 timepoints) and activated status (activated versus resting),
- ix. Count of memory T cells as a function of time (over 14 timepoints) and type of memory cells (effector versus central memory versus terminally differentiated effector memory,
- x. Count of B cells as a function of time (14 timepoints) and activated status (activated versus resting),
- xi. Count of myeloid suppressor cells as a function of time (14 timepoints) and PDL-1+/-status,

For these count variables, Poisson Regression Analysis based on generalized estimating equations (GEE) method will be performed by utilizing the procedure PROC GENMOD SAS 9.4 with Poisson distribution, log link function and independent covariance structure.

Continuous variables such as cytokine levels (GM-CSF, IL-1b, IL-1RA, IL-2, IL-2R, IL-4, IL-5, IL-6, IL-7, IL-8, IL-10, IL-12, IL-13, IL-15, IL-17, TNF alpha; MCP-1, MIP1a, MIP1b, MIG, RANTES, IFN-alpha, IFN-gamma, IP-10, Eotaxin) will be examined over time (14 timepoints) using mixed model repeated measures (MMRM) by utilizing PROC MIXED SAS 9.4. In both of the models to be fit to these immune markers, the status of infection as a time-dependent covariate will be included to examine the effect of both time and infection on cell cytokine levels.

8.3.5 Longitudinal analysis of the gut microbiome.

The time points of stool sample collection are:

- 1) Screening Visit (up to 7 days post consent). If patient signs consent within 7 days of transplant admission, stool sample collection will start from item "2" (Preconditioning)
- 2) Preconditioning (to be collected within 48 hours prior to transplant admission)
- 3) Engraftment, (within 72 hours of ANC > 500)

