- 4) Day 1 of Week 1 of combined checkpoint therapy.
- 5) Day 1 of Week 4 of combined checkpoint therapy,
- 6) Day 1 of Week 7 of combined checkpoint therapy,
- 7) Day 1 of Week 12 of combined checkpoint therapy.
- 8) Day 1 of Week 18 of combined checkpoint therapy, and
- 9) Day 1 of Week 26 of combined checkpoint therapy.
- 10) End of Treatment Visit
- 11) Post-transplant, 9 months,
- 12) Post-transplant, 12 months,

Amendment9 09NOV2021 Page 40 of 77

- 13) Post-transplant, 15 months.
- 14) Post-transplant, 18 months and / or
- 15) Relapse, as it occurs.

Counts of specific intestinal microbial strains will be examined overtime (15 time points) using Poisson regression analysis utilizing PROC GENMOD as described in analysis of blood immune markers. In each of the models for each microbial strain, status of infection as a time-dependent covariate will be included as microbial along timepoint variable.

The overall microbial composition will be determined by 16S rRNA miSeq Illumina platform and analyzed by Second Genome Solutions proprietary 16S bioinformatic data analysis software package.

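### The strain model in section 8.3.5 has time and infection as its only terms, so it does not estimate the strain-outcome association that the microbiome objective names

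*Combined protocol and SAP*

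**What the plan says.** The microbiome objective appears in the synopsis, section 1.0 and section 8.0, for Phase Ib and for Phase IIA: "To identify specific intestinal microbial strains associated with improved outcome in autologous stem cell transplantation patients treated with combined checkpoint inhibitors". None of these places says which outcome is meant.

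Section 8.3.5 lists 15 stool sampling times, from screening to month 18, ending with "15) Relapse, as it occurs". The strain analysis follows: "Counts of specific intestinal microbial strains will be examined overtime (15 time points) using Poisson regression analysis utilizing PROC GENMOD". For each strain's model, the section adds that "status of infection as a time-dependent covariate will be included as microbial along timepoint variable". It refers back to the blood marker analysis in section 8.3.4 for the method, which is GEE "with Poisson distribution, log link function and independent covariance structure".

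Two other microbiome steps are described. Overall composition is to be "analyzed by Second Genome Solutions proprietary 16S bioinformatic data analysis software package" (section 8.3.5). Section 1.0 adds that "quantitative real-time PCR analysis will validate the specific microbial strains identified by miSeq".

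**The concern.** The objective asks whether strain abundance differs between patients who do well and patients who do not. The model asks whether strain abundance changes over the visits and with infection. Those are different questions, and followed exactly the plan answers only the second.

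The protocol asks for stool at up to 15 times per patient largely to serve this objective. If the outcome analysis is left to be devised later, the outcome, the sample and the strains reported could all be chosen after the data have been seen. Any strain then named would carry less weight than the sampling effort deserves.

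**Working it through.** **1. Objective against model**

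| Element needed for the objective | What the plan provides |
|---|---|
| Defined outcome | Not defined in the synopsis, 1.0, 8.0 or 8.3.5 |
| Strain measure | Strain count, as dependent variable (8.3.5) |
| Term linking strain to outcome | None; covariates are time point and infection (8.3.5) |
| Outcome analysis elsewhere that uses strains | None in 8.3.1 to 8.3.3 or in 8.4 |
| Outcome comparison in the 16S software step | None stated; it is assigned to overall composition |
| Outcome comparison in the qPCR step | None; it confirms strains already identified |

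**2. Parameters of the stated model**

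log E(count) = intercept + time (15 levels) + infection

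Number of parameters = 1 + (15 − 1) + 1 = 16. None compares patients by outcome.

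**3. Can the relapse level stand in for outcome?**

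With an independence working structure and a separate level for each time, a time contrast is in effect a ratio of mean counts at two times, adjusted for infection. Two cases were compared. The values are assumptions, not figures from the documents: half the patients relapse, relapse ends a patient's scheduled samples, and infection is equally common in both groups.

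- Case A: the strain is constant within each patient, at 50 in relapsers and 150 in non-relapsers. Screening mean = (50 + 150)/2 = 100. Relapse-sample mean = 50. Ratio = 50/100 = 0.50.
- Case B: the strain does not differ by outcome at any scheduled visit. It is 100 in everyone and falls to 50 only in the relapse sample. Ratio = 50/100 = 0.50.

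The relapse contrast is the same in both cases, so it cannot tell a strain that differs between outcome groups from one that merely changes at relapse.

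In Case A the month-18 contrast is 150/100 = 1.50, because only non-relapsers remain. It looks like a rise over time although no patient's count has changed. This part depends on sampling stopping at relapse. Section 8.3.4 treats relapse as a possible last time point for the blood samples, but sections 5.8 and 5.9 are less clear on whether stool collection continues.

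With an outcome term added and scheduled samples only, the relapser to non-relapser ratio is 50/150 = 0.333 in Case A and 100/100 = 1 in Case B.

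**4. Simulation of the same cases**

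Poisson GEE with independence structure; 2000 patients; infection at 15% of samples with rate ratio 0.8 (all assumed).

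| Quantity | Case A | Case B |
|---|---|---|
| Relapse vs screening, stated model | 0.499 | 0.499 |
| Month 18 vs screening, stated model | 1.50 | 1.00 |
| Relapser vs non-relapser, outcome term added | 0.335 | 1.001 |

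The fitted values agree with the arithmetic in step 3.

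**The case against.** The best defence is that relapse is in the model, as the fifteenth time level, so a reader who concludes that the analysis holds no outcome-related information at all goes too far. That stands: the contrast describes the relapse sample. It still does not estimate the objective, because it has no progression-free comparator and mixes differences between patients with change at relapse.

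It may also be said that the proprietary 16S software could compare outcome groups. It might, but the plan does not say so.

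Several stronger criticisms are tempting and are not supported.

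- **Sequencing depth.** A reader might infer that differences in read depth will appear as strain effects because no offset is given. That assumes the modelled counts are unnormalised 16S reads. Section 8.3.5 does not give their source, and section 1.0 also brings in quantitative PCR for specific strains. What can be said is that the source and normalisation are not stated.
- **Choice of Poisson.** Overdispersion alone does not make the method wrong, since GEE is normally reported with empirical standard errors. Another distribution would be a preference.
- **Number of false positives.** The documents give neither the number of strains nor a threshold for declaring one, so no count can be put on this. The absence of multiplicity control across one model per strain is a fair secondary point; qPCR confirmation does not replace it.
- **A yes/no PFS18 covariate as the remedy.** This has no value for patients censored before 18 months, and section 8.5 allows for withdrawal and loss to follow-up.

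Finally, the objective is tertiary, and no expansion, stopping or efficacy rule uses it. That stands and limits the weight of the point.

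**Conclusion.** The mismatch is real. The stated model describes strain change over time and with infection. It has no outcome term among its 16 parameters, the outcome is undefined, and no other section fills the gap. This rests on the text alone and needs no numerical assumption. The illustrative ratios do rest on assumed values; they show only that the relapse level cannot serve as a substitute.

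The point should be settled before strain data are examined. A reader might infer that the trial's main results are in doubt, but the primary safety and PFS18 analyses do not use the microbiome data and are unaffected.

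**What to change.** In section 8.3.5:

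1. Define the outcome for this objective as PFS in section 8.3.3.
2. Add a strain-outcome analysis. One suitable form models PFS on strain abundance at a single prespecified pre-checkpoint sample, used as a landmark. It would include patients progression-free at that sample, treat censoring as in 8.3.3, and stratify by disease group. Week 1 Day 1 is a reasonable choice; the screening stool is less so, because 8.3.5 omits it for patients who consent within 7 days of transplant admission.
3. Restrict this analysis to patients with PFS follow-up. The synopsis and section 2.1 limit the remaining follow-up of Groups E and F to safety and correlative work, so their stool may have no matching PFS outcome.
4. Keep the time and infection model, labelled as descriptive.
5. As a secondary matter, apply Benjamini-Hochberg false-discovery control across strains.
6. State whether the counts are 16S reads or qPCR quantities and how they are normalised. Use a log(total reads) offset only if they are unnormalised reads.

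The change adds no visits or samples. It costs some SAP wording and analysis work, and fewer strains will be declared. Precision will be low. Phase Ib has 4 × 7 = 28 planned patients in Groups A to D. At the 40-50% PFS18 that section 8.1 expects without checkpoint inhibitors, that is 28 × 0.50 = 14 to 28 × 0.60 ≈ 17 events by 18 months; at the 57% target it is 28 × 0.43 ≈ 12. The Phase Ib results should therefore be reported as exploratory.

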8.4 Additional Endpoint Analyses

8.4.1 Toxicities of the treatments

The toxicity of combined checkpoint inhibition with nivolumab and ipilimumab after autologous hematopoietic stem cell transplantation in patients at high risk for post-transplant recurrence will be evaluated for all adverse events with grade 3 or grade 4 observed in each cohort and presented as counts (proportion) and corresponding exact binomial 95% confidence intervals for proportion.

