8.2 Populations for Analysis

- The All-Subjects-as-Treated (ASaT) population will be employed for safety analyses. Descriptive tables that summarize the number and percentage of subjects that experience adverse events as categorized in the NCI CTCAE Version 4.03 will be generated by cohort/group.
- The intent-to-treat (ITT) population will be employed for response and PFS analyses.
 Descriptive tables that summarize the number and percentage of subjects with responses and PFS will be generated by cohort/group.

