8.3 Statistical Methods

8.3.1 Safety Analysis

The safety of combined checkpoint inhibition with nivolumab and ipilimumab, after autologous hematopoietic stem cell transplantation in patients at high risk for post-transplant recurrence, will be evaluated for composite endpoint (at least one treatment-related toxicity and all adverse events observed in each cohort and presented as counts (percentages) and corresponding exact binomial 95% confidence intervals for proportion. Adverse events will include Immune-mediated colitis, hepatitis, endocrinopathies, nephritis, rash, encephalitis and immune-related AEs (irAEs).

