8.3.3 Progression Free Survival at 12, 18 months

Progression-free survival (PFS) is defined as time interval from date of transplantation to pathologic disease progression or death from any cause. PFS of patients at high risk for post-autologous stem cell transplant recurrence in each cohort will be estimated using Kaplan-Meier method and probabilities will be calculated for months 12 months and 18 months, along with 95%. In Phase II, if PFS18 is at least 52% then study will have demonstrated the early efficacy that was sought in that particular cohort, i.e. PFS18 ≥ 57%.

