8.4.3 General Data Analysis

The summary of the demographic characteristics will be presented. Continuous variables will be summarized using mean (SD) or median (interquartile range) depending on whether or not the data follow the normal distribution. Categorical variables will be summarized by frequency (percentage). All adverse events will be presented as listings. All analysis will be performed using SAS version 9.4 (SAS Institute Inc. Cary, NC, USA).

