 - Grade 3 drug-related uveitis, pneumonitis, bronchospasm, diarrhea, colitis, neurologic adverse event, hypersensitivity reaction, or infusion reaction of any duration requires discontinuation
 - Grade 3 drug-related laboratory abnormalities do not require treatment discontinuation except those noted below
 - Grade 3 drug-related thrombocytopenia > 7 days or associated with bleeding requires discontinuation
 - Any drug-related liver function test (LFT) abnormality that meets the following criteria require discontinuation:
 - AST or ALT > 8 x ULN
 - Total bilirubin > 5 x ULN
 - Concurrent AST or ALT > 3 x ULN and total bilirubin > 2 x ULN
- Any Grade 4 drug-related adverse event or non-hematological laboratory abnormality, except for the following events which do not require discontinuation:
 - Isolated Grade 4 amylase or lipase abnormalities that are not associated with symptoms or clinical manifestations of pancreatitis and decrease to < Grade 4 within 1 week of onset.
 - Isolated Grade 4 electrolyte imbalances/abnormalities that are not associated with clinical sequelae and are corrected with supplementation/appropriate management within 72 hours of their onset
- Any Grade 5 drug-related death

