9.6 Assessment of Toxicity

Common Terminology Criteria for Adverse Events (CTCAE) will be used for the assessment and grading of all toxicities experienced by patients enrolled into this study (http://ctep.cancer.gov/forms/CTCAE Index.pdf)

If the nature of the adverse experience is listed in the CTCAE, the maximum grade will be reported.

If the adverse experience is not listed in the NCI CTCAE Common Terminology Criteria Adverse Events, report the toxicity grade using the following criteria:

- Grade 1 = Mild: an adverse experience which is easily tolerated by the patient, causing minimal discomfort and not interfering with everyday activities.
- Grade 2 = Moderate: an adverse experience which is sufficiently discomforting to interfere with normal everyday activities.
- Grade 3 = Severe: an adverse experience which is incapacitating and prevents normal everyday activities.

- Grade 4 = Life Threatening: an adverse experience which places the patient at immediate risk of death.
- Grade 5 = Death

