APPENDIX D: STUDY FLOWCHART

	Screening	Treatment	Safety	End of			
	Phase	cycles	Visits	treatment	P	ost treatmen	t
	Screening (Visit 1)	Day 1 (+/- 2 days) of weeks 1, 4, 7, 10, 12, 14, 16, 18, 20, 22, 24, 26 Week 1 is defined as initiation of checkpoint inhibitors, not weeks post	Day 1 (+/- 2 days) of weeks 2, 3, 5, 6, 8, and 9 Week 1 is defined as initiation of checkpoint inhibitors, not weeks post ASCT.	For study completion or discontinuation of therapy (discon) (To be completed within 2 weeks of last dose) (+/- 14 days)	Safety visit 30 days post End of Treatment Visit (+/- 14 days)	Follow up visits every 12 weeks post End of Treatment Visit (+/- 14 days)	Survival visits every 12 weeks post End of Treatment (+/- 14 days)
		ASCT.	post ASC1.				
		1	Administrativ	e Procedures			
Informed Consent	Xa						
Informed Consent for Future Biomedical Research - Optional	Xn						
Inclusion/Exclusion Criteria	X						
Demographics/Medical History	Xa						
Prior and Concomitant Medication Review	X	Х	Х	X	Х	Xg	
Trial Treatment Administration (See Section 5.0)		х					
Post-study disease status				Х	X	Х	
Survival Status							X ^h
		С	linical Procedu	res/Assessments			
Review Adverse Events	Χ	Х	X	X	X	Xa	
Physical Examination	X d	Х	Х	Х	Х	Х	
Vital Signs and Weight	X d	Х	Х	Х	Χ	Х	
12-Lead Electrocardiogram	Xp						
MUGA or ECHO with	Xp						
Imaging Assessment ^e	X ^{b, e}						
Pulmonary Function Test	Xp						
ECOG PS	Χď	Х		Х	Х	Х	
			Laboratory /	Assessments			
CMV, HIV, HTLV, Hepatitis B, Hepatitis C evaluations	Χď						
Pregnancy Test ^c	X ^d	X		X	Х		
CBC with differential	X ^d	Х	Х	X	Х	Х	

Complete Metabolic Panel (Na, K, BUN, Creatinine, Cl, CO2, Anion Gap, Ca, P, Mg, Uric Acid, Alk Phos, AST, ALT, bilirubin, albumin, LDH, Glucose, GGTP).	Xq	Х	х	х	х	Х	
Total CK	X d	X			Х		
LFTs (PT/INR, aPTT, albumin, total bilirubin)	X^d						
Baseline disease assessments	X ^{d, f}						
Urinalysis	Χď	On weeks 1,7,14,22 and 26 only		Х			
Haptoglobin	X d	On weeks 1, 7, 12, 16, 20, and 24 only			х		
TSH, T3 and free T4; lipase and amylase, cortisol	Χď	On weeks 1,7,14,22 and 26 only		х			
Bone Marrow Biopsy / Tumor Biopsy	X^k			Xk			
Peripheral blood collection for blood immune phenotype and metabolomics analysis	Χ ^L	X On weeks 1, 4, 7, 12, 18 and 26 only				Post transplant months 9, 12,15 and 18 and at time of relapse	
Stool sample for microbiome analysis	Χ ^m	X On weeks 1,4, 7, 12, 18 and 26 only				Post transplant months 9, 12,15 and 18 and at time of relapse	

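### The section 8.4.1 toxicity table stops at grade 4, so a patient whose only high-grade event is fatal is left out of its severe-toxicity proportion

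*Combined protocol and SAP*

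**What the plan says.** Determining the toxicities of the treatments is a secondary objective in both Phase Ib and Phase IIA (sections 1.0 and 8.0). The analysis under the matching heading, 8.4.1, is limited by grade: toxicity will be "evaluated for all adverse events with grade 3 or grade 4 observed in each cohort", as counts with exact binomial 95% confidence intervals.

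On grading, section 9.6 says: "If the nature of the adverse experience is listed in the CTCAE, the maximum grade will be reported". The scale in the same section, for events that CTCAE does not list, makes grade 5 death.

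Other parts of the plan also reach fatal events:

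- Section 8.2 plans tables by cohort, in the as-treated population, of subjects with adverse events by CTCAE category. It sets no grade limit.
- Section 8.3.1 covers the composite safety endpoint and "all adverse events observed in each cohort and presented as counts (percentages"), with exact intervals and again no grade limit.
- Section 8.4.3 adds: "All adverse events will be presented as listings".
- The Phase Ib safety endpoint counts treatment-related non-hematologic toxicity of grade 4 or above. The Phase IIA definition of unacceptable toxicity in section 8.6 includes "Any Grade 5 drug-related death".
- Section 8.3.3 defines PFS as the "time interval from date of transplantation to pathologic disease progression or death from any cause". Section 8.2 assigns its population: "The intent-to-treat (ITT) population will be employed for response and PFS analyses".

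The flowchart in Appendix D also schedules "Survival visits every 12 weeks post End of Treatment (+/- 14 days"). Overall survival is not an objective in either phase.

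**The concern.** A table of severe toxicity is normally read as covering grade 3 and above. This one has an upper limit as well as a lower one, so the worst outcome is the one it does not count. A reader who takes the 8.4.1 proportion and interval as the severe-toxicity rate of a cohort would have a figure that is too low whenever a patient died of an event and had no other grade 3 or 4 event.

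The gap looks unintended, because the Phase Ib endpoint and the Phase IIA stopping criterion both reach grade 5. It matters here because the stated goal includes safety, the regimen is an immune combination started within weeks of transplant, and the protocol's own background (section 3.1.5) reports fatal pneumonitis with these drugs in other tumor settings.

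A smaller, related point is that survival status is collected every 12 weeks, but section 8 plans no use of it except through death as a PFS event. A death after progression therefore enters no efficacy analysis, and PFS at 18 months does not show how many failures were relapses and how many were deaths.

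**Working it through.** The plan states no figure to reproduce. The check is a reading of the rules side by side, followed by an illustration.

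**Step 1: the rules together.** Section 8.4.1 counts grades 3 and 4. Section 9.6 carries an event at its maximum grade, and a fatal event is grade 5. An event that began at grade 3 or 4 and ended in death is therefore a grade 5 event and falls outside 8.4.1. The patient stays in the table only through some other grade 3 or 4 event.

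**Step 2: where a fatal event still appears.**

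| Place | Grade 5 included? | Limit |
|---|---|---|
| 8.2 as-treated tables | Yes | No grade breakdown specified |
| 8.3.1 all-event counts | Yes | No grade breakdown specified |
| 8.4.3 listings | Yes | Listing, not a proportion |
| Phase Ib safety endpoint | Yes | Treatment-related and non-hematologic; pooled with grade 4 |
| Phase IIA stopping criterion | Yes | Drug-related; pooled with non-fatal events |
| 8.4.1 severe-toxicity table | No | Grades 3 and 4 only |

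Fatal events are reported, but no planned table specifies a line for them, and the one table restricted to severe events leaves them out.

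**Step 3: size.** Inputs are the cohort sizes of 7 (Phase Ib) and 37 (Phase IIA) from section 8.1, and the exact binomial interval that 8.4.1 prescribes. The plan gives no fatal-event count for this population, so the counts below are assumptions.

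For x events in n patients, the exact 95% limits are the 2.5% point of Beta(x, n − x + 1) and the 97.5% point of Beta(x + 1, n − x). For x = 0 the lower limit is 0 and the upper limit is 1 − 0.025^(1/n), which gives 0.0949 for n = 37 and 0.4096 for n = 7.

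| Assumed case | 8.4.1 as written | Grade 3 to 5 |
|---|---|---|
| One fatal event, no other high-grade event, n = 37 | 0/37 = 0% (0 to 9.5%) | 1/37 = 2.7% (0.07 to 14.2%) |
| The same, n = 7 | 0/7 = 0% (0 to 41.0%) | 1/7 = 14.3% (0.4 to 57.9%) |
| Nine patients with grade 3 to 5 events, one of them fatal only, n = 37 | 8/37 = 21.6% (9.8 to 38.2%) | 9/37 = 24.3% (11.8 to 41.2%) |

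Each omitted patient moves the proportion by 1/37 = 2.7 points or 1/7 = 14.3 points.

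**The case against.** The strongest reply is that fatal events are already covered. The tables in 8.2 and 8.3.1 have no grade limit, all adverse events are listed, and the endpoints that drive decisions include grade 5. Nothing makes 8.4.1 the only analysis of the toxicity objective; it sits under additional endpoint analyses. The numerical effect is hypothetical, arises only if the patient has no other grade 3 or 4 event, and in the larger example the two intervals overlap almost entirely.

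Most of this stands. A reader might infer from 8.4.1 that deaths go unreported or unmonitored, and the documents do not support that. What the reply leaves untouched is that the severe-toxicity proportion is incomplete by its own wording.

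On survival, the reply is that overall survival is not an objective, and that death from any cause already counts in the primary efficacy endpoint. Relapse-free patients also have month-18 imaging and sampling (section 6.2.1, Appendix D). That too stands. A reader might go on to ask for a formal survival endpoint, competing-risk estimates or a fixed end date for survival contacts, but no stated objective depends on them. Competing-risk estimates would also rest on the requirement in 8.3.3 that progression be pathologic, so a relapse never biopsied could be counted as death without progression. Because section 6.2.3 calls for a confirmatory biopsy, such cases should be exceptions.

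**Conclusion.** The point holds as a narrow reporting gap. Section 8.4.1 as worded excludes grade 5, so its severe-toxicity proportion and exact interval omit any patient whose only high-grade event was fatal. The size is 2.7 points per such patient in a cohort of 37 and 14.3 points in a cohort of 7. This rests on a literal reading of 8.4.1, on the maximum-grade rule in 9.6, and on assumed counts. The gap affects no sample size, stopping boundary or expansion decision.

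The lack of a planned summary of deaths is secondary. Describing them would help readers interpret PFS, but leaving them out breaks no stated objective.

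**What to change.** In section 8.4.1, replace the restriction to grade 3 or grade 4 with grade 3 to 5, and show grade 5 as its own row, with the same counts and exact intervals. This is a wording change that uses data already collected.

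Optional and descriptive only, by cohort: report the number of deaths; list deaths with cause where known; and split PFS events into progression and death without progression, using the definition in 8.3.3. The data come from survival status and progression records already scheduled. Appendix D allows survival status to be taken by telephone, so cause of death may need one extra question and will sometimes be unknown. The cost is a few added tables or listings, with no new clinic visit and no change to sample size or decision rules.
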